7.3 MISSING, UNUSED AND SPURIOUS DATA

There will be no data imputation for missing data in the primary endpoint (time to healing) and the secondary endpoint of ulcer free time. Any imputation methods used may be proposed for purposes of sensitivity analysis for other secondary outcomes, including ulcer healing rate, QoL and markers of clinical success. Imputation methods will be fully documented in the SAP.

7.4 DEVIATIONS FROM THE STATISTICAL ANALYSIS PLAN

Any deviation(s) from the final statistical analysis plan in the final analysis will be described and justification given in the final report.

7.5 HEALTH ECONOMIC ANALYSIS

The economic evaluation will be based on both a modelling exercise and a patient level in-trial analysis. The main analyses will be performed from the perspective of the NHS and Personal Social Services. Secondary analyses will be performed from a societal perspective. The price year will be 2017-18. Discounting will be applied according to UK Government guidelines. The study will be reported according to current guidelines for economic evaluation (CHEERS).

The within-trial analysis will compare early versus delayed endovenous treatment of superficial venous reflux in patients with chronic venous ulceration, within the time-horizon of the extended trial. Data will be collected by case note review and questionnaires completed at baseline, 6 weeks, 6 months, 12 months and at a single time point during October 2018 and March 2019. Resource use items in hospital and community care related to the treatment of venous ulceration, adverse events or complications will be recorded for each patient at each follow-up. Resource use will be multiplied by UK unit costs obtained from published literature, Healthcare Resource Groups (HRG) costs, and manufacturers' list prices to calculate overall

costs. A standard tariff will be applied for each bandage change. Utilities (QALYs) will be calculated from the EQ-5D questionnaire administered to patients at each follow-up. The extent of missing data will be assessed and appropriate methods to handle missing data will be applied. The incremental cost-effectiveness ratio will be calculated and compared to current UK decision making thresholds. Sensitivity analysis will be carried out to test the robustness of results to alternative assumptions (for example, about missing data, or using per-protocol estimates of treatment effect) or alternative data (for example, about unit costs). Probabilistic sensitivity analysis will be carried out using bootstrapping.

A decision model will also be constructed to take into account outcomes that might be expected to occur beyond the timeframe of the RCT (e.g. recurrence, healing), the results of other RCTs that have assessed early or delayed endovascular therapy for treating venous ulcers, or any relevant comparators that are not considered in the RCT (e.g. surgery, bandaging only). The health states used in the model will be based on the natural history of chronic venous ulcers, to be obtained from the trial, from the literature and from expert opinion. . The inputs for the model will be the transition rates for moving from one state to another, the relative risks for each treatment compared with usual care, and the costs and HRQOL associated with each health state. Use of secondary and primary care patient resource use and EQ-5D responses associated with health states will be estimated mainly from the trial. Sensitivity analyses will be carried out to test the robustness of the model results to alternative assumptions and alternative data. Probabilistic sensitivity analysis will be carried out using Monte-Carlo simulation.

7.6 LOSSES TO FOLLOW-UP AND PROTOCOL VIOLATIONS

The primary assessment involves intention-to-treat analysis. Therefore, strenuous efforts will be made to ensure that only patients willing to undergo either immediate or delayed superficial venous ablation and compression bandaging are randomised. Monthly reports of protocol violations will be provided by local sites to the trial coordinators, who reserve the right to suspend or exclude sites in the event of wilful protocol violations. Similarly, efforts will be made to obtain complete follow-up for all randomised participants (irrespective of whether or not they underwent allocated treatment). For those participants unable or unwilling to attend follow-up appointments, home-visits or follow-up by community nurses may be considered.

A high rate of protocol violation was seen in previous trials of venous ulceration (including the ESCHAR trial). This is likely to reflect the reluctance and apprehension of elderly patients to undergo surgical interventions involving general anaesthesia. The modern management of superficial venous disease involves a range of minimally invasive, endovenous modalities that can be performed using local or no anaesthesia. Procedures are performed on an outpatient basis and can be

completed in around 30 minutes. Published studies of endovenous interventions have demonstrated excellent patient satisfaction and few treatment refusals. Due to the published evidence and extensive personal experience among the research team, the rate of participation should be higher and rate of protocol violations lower than previous studies.

The following will be recorded as protocol deviations:

- 1) Patients randomised to multilayer compression / stockings plus early venous reflux ablation, who receive endovenous intervention more than two weeks from randomization.
- 2) Patients who are non-compliant with compression bandaging, defined as use <75% of the prescribed duration.
- 3) Patients randomised to compression bandaging alone who undergo endovenous ablation prior to verified healing.

8. ADVERSE EVENTS

8.1 REPORTING PROCEDURES

During the first 12 months all serious adverse events and all intervention-related adverse events should be reported. Any serious adverse events reported at the October 2018 to March 2019 follow-up time point should be reviewed by the Principal Investigator to assess whether they are related to the treatment pathway and only related events should be reported to the sponsor via INFORM. Depending on the nature of the event the reporting procedures below should be followed. Any questions concerning adverse event reporting should be directed to the Chief Investigator in the first instance.

8.2 RELATED ADVERSE EVENTS

Patients randomised to early venous intervention have the potential risks of treatment. Competent, experienced medical staff will perform all procedures and every effort will be made to prevent adverse effects. The adverse events listed below are expected to be related to the endovenous interventions used in the trial and should be reported. **Please note this is not an exhaustive list, if you suspect an event is related to treatment please contact the Trials Unit.**

Systemic

- **allergic reaction req. local / no treatment**
- **migraine**
- **visual disturbance**
- **fainting**
- **Cough / chest tightness**
- **Systemic infection**
- **PE**
- **TIA**
- **Stroke**

Local

- **Bleeding requiring intervention**
- **Blistering of skin**
- **Pressure damage**
- **Nerve damage**
- **DVT**
- **Hematoma**
- **Patient reported paresthesia**
- **Pigmentation of skin**
- **Superficial thrombophlebitis**
- **New ulcer**
- **Deterioration of ulcer**
- **Wound infection**

8.3 NON SERIOUS ADVERSE EVENTS

All such events, which are judged by the local PI to be related to the interventions, whether expected or not, should be recorded in InForm

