4.1 PATIENT RANDOMIZATION

The normal clinical team will make initial contact with potentially eligible patients at the referral visit.

Those who consent will be registered on the InForm ITM (Integrated Trial Management) System, a web-based data entry system, which is maintained by ICTU, and their eligibility for the study confirmed. A randomization list will be loaded onto the InForm system for each centre (as stratification will be by centre) before recruitment commences, having been prepared in advance by a statistician who is independent of the study. Each potential participant, if confirmed to be eligible, will be assigned the next available entry in the appropriate randomization list (i.e. without foreknowledge). Thereafter, treatment allocation will not be blinded (with the exception of assessment of ulcer healing – see 4.3.1). For patients with bilateral venous ulceration, the worst leg (according to the patient) will be designated the ‘reference leg’. Interventions may be performed on both legs, if deemed appropriate by the responsible clinician.

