7.2 PLANNED ANALYSES

No formal interim analyses are planned. Informal interim analyses will be performed if requested by the Data Monitoring Committee (DMC) but findings will be made available to member of the DMC only. Basic descriptive methods will be used to present the data on study participants, trial conduct, clinical outcomes and safety (in total and for each study group separately). The primary outcome will be time to complete healing. We will test the hypothesis that there is no difference in time to complete healing between the control and intervention groups using a log-rank test

(two-tailed, 5% significance level). Kaplan-Meier survival curves will also be presented and we will perform a subsidiary analysis investigating the effect of study centre, participant age, ulcer size and chronicity on time to complete healing using Cox regression. To adjust for potential surgeon and centre effects, surgeon and centre will be included in the Cox regression analysis as random effects. All analyses will be on an intention-to-treat basis. If there is substantial cross-over, per-protocol analyses may be explored for sensitivity analyses. Safety and tolerability data will be presented by the two arms on an intention-to-treat basis. The statistical analysis plan (SAP) for the original trial (follow up to 1 year) will be finalised prior to the final analysis. An additional SAP for the extension follow-up (up to 5 years) will be finalised before the analysis of extension data.

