Appendix 1: Summary of assessments and follow-up visits

Time point	Estimated duration (mins)	Clinical evaluation*	Telephone follow-up**	Wound review/photo /tracing***	Collection of further endovenous intervention / duplex report	Venous duplex	Randomisation	Consent	Health Questionnaires (EQ-5D, SF-36, AVVQ)
Screening Visit	45	X				X		X ^a	
Baseline Visit	60-90	X		X***			X	X ^b	X
1 month	30		X						
6 weeks	60-90	X		X ^{?****}		X ^c			X
2 months	30		X	X [?]					
3 months	30		X	X [?]					
4 months	30		X	X [?]					
5 months	30		X	X [?]					
6 months	30		X	X [?]					X
7 months	30		X	X [?]					
8 months	30		X	X [?]					
9 months	30		X	X [?]					
10 months	30		X	X [?]					
11 months	30		X	X [?]					
12 months	30		X	X [?]					X
Extension follow-up Oct18 to Mar 19	240	X ^d	X		X			X ^e	X

*. Demographic details (age, sex, ethnicity), Pregnancy test for woman of child bearing potential. General clinical details (body mass index, ankle brachial pressure index – performed within previous 4 weeks, comorbidities, medication history). Ulcer details (duration, progression, previous ulcer history, size of current ulcer – using photography and planimetry). Details of venous disease (previous deep vein thrombosis, previous venous interventions, pattern of venous reflux on duplex)

. Ulcer healing assessment, compression type, AE assessment, Concomitant medications, health resource use. *tracing only performed at baseline & 6 weeks

a. Approached b Taken c. Only for those who have early endovenous treatment d. review of clinical notes only e. patients will not be reconsented as already consented for longer term follow-up at outset but will be asked if they wish to continue

?dependant on whether the ulcer has healed photo will be taken at verification visit and taken weekly for 4 weeks, unless otherwise confirmed by the trial manager. Once the ulcer has healed the patient will still be followed up with monthly phone calls.

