#### **4.8 Safety Data**

The safety data, including adverse events (AEs) and serious adverse events (SAEs) will be provided in a tabular format for the two arms (Table 11 and Table 12). AEs will be summarised by description and outcome and SAEs will be summarised by SAE reason, frequency, severity, and relationship to treatment, outcome and expectedness.

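### Non-serious adverse events are filtered on relatedness by an unblinded investigator but tabulated by randomised arm, so SAP Table 11 is open to differential ascertainment, probably against early ablation

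*Protocol*

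**What the plan says.** Protocol 8.1 sets the general rule: "During the first 12 months all serious adverse events and all intervention-related adverse events should be reported". Section 8.3 applies it to non-serious events, namely those "which are judged by the local PI to be related to the interventions, whether expected or not, should be recorded in InForm". It does not define the interventions it means.

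Section 8.2 opens with the risks to patients allocated to early treatment and then introduces its list: "The adverse events listed below are expected to be related to the endovenous interventions used in the trial and should be reported". The list includes "Deterioration of ulcer", and also new ulcer, wound infection, pressure damage, blistering and DVT.

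On blinding, Protocol 4.1 states that "treatment allocation will not be blinded (with the exception of assessment of ulcer healing", so the person judging relatedness knows the arm.

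On presentation, Protocol 7.2 says: "Safety and tolerability data will be presented by the two arms on an intention-to-treat basis". SAP 4.8 says that AEs and SAEs "will be provided in a tabular format for the two arms". Table 11 has one column per arm with its N. Its title calls it only a summary of adverse events, and it has no row for relatedness. Table 12, for SAEs, does have one.

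Two provisions run the other way. Protocol 8.4 has SAEs recorded to 12 months whether related or not. The telephone follow-up in Protocol Appendix 1, monthly and without restriction by arm, covers "Ulcer healing assessment, compression type, AE assessment, Concomitant medications, health resource use".

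**The concern.** Several listed events are part of the ordinary course of a leg ulcer under compression. If relatedness means relatedness to an endovenous procedure, a compression-arm patient who has not yet been ablated cannot have a related event. The same infection or ulcer deterioration could then be entered for an early-arm patient and left out for a compression-arm patient.

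The window for a recordable event also differs by arm. It opens within about two weeks of randomisation in the early arm. In the compression arm it opens only after confirmed healing, at six months, or on clinical deterioration (Protocol 5.4), and for some patients perhaps never.

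At stake is how Table 11 is read. It looks like a randomised comparison of all adverse events. If it is really a count of events attributed to treatment, it may make early ablation look less safe than it is, and nothing in the table lets a reader see or undo the filter.

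**Working it through.** The documents give no adverse-event rate and no safety power figure, so there is no plan figure to reproduce. The check is a comparison of the texts, followed by an illustration on assumed values.

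**Texts side by side**

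| Question | Where | Answer |
|---|---|---|
| Which non-serious events are recorded? | Protocol 8.1, 8.3 | Those judged related |
| Related to what? | Protocol 8.2 | Endovenous interventions; undefined in 8.3 |
| Is PI judgement needed for listed events? | Protocol 8.2 v 8.3 | 8.2 says report them, with no such condition; 8.3 requires judgement |
| Is the local PI blinded? | Protocol 4.1 | No |
| How are they shown? | Protocol 7.2, SAP 4.8, Table 11 | By randomised arm, intention to treat |
| Are SAEs to 12 months filtered? | Protocol 8.4 | No |

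The filter, the open judgement and the two-arm table are all in the documents. Whether the filter works differently in the two arms depends on how sites read 8.2 and 8.3 together.

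**Illustration**

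Inputs: N = 450/2 = 225 per arm (target in Protocol 7.1, 1:1 allocation). Assumed, not in the documents: the same true proportion p of patients with an event in both arms, and a probability a that the PI calls the event related.

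Expected recorded patients = N × p × a. The recorded ratio, early to compression, is a(early)/a(compression), whatever p and N are.

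With p = 0.30 there are 225 × 0.30 = 67.5 patients with a true event in each arm. With a(early) = 0.50, the early arm records 67.5 × 0.50 = 33.8.

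| a(compression) | Recorded, compression | Ratio | Chance of nominal p < 0.05 |
|---|---|---|---|
| 0 | 0 | no finite value | near 100% |
| 0.25 | 67.5 × 0.25 = 16.9 | 2.0 | 71% |
| 0.40 | 67.5 × 0.40 = 27.0 | 1.25 | 15% |
| 0.50 | 67.5 × 0.50 = 33.8 | 1.0 | 5% (no bias) |

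The last column is for a two-sided comparison of proportions. It only gives a sense of scale, because the SAP plans no such test. At p = 0.10 and p = 0.50 the 0.50 v 0.25 case keeps its ratio of 2.0, with chances of 29% and 93%.

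If events are recorded whatever their attribution, a = 1 in both arms. Each arm then records 67.5 and the ratio is 1.0.

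**The case against.** The strongest reply is that the undercount is not built in. Section 8.3 does not define the interventions, and Protocol section 5, on the details of interventions, covers compression as well as ablation. Section 8.2 can be read as making the listed events reportable without PI judgement. The filter also drops early-arm events that the PI thinks unrelated. All of this stands. A reader might infer that the compression arm must be undercounted; the documents support likely, not certain. The same ambiguity also means that sites may apply different rules, which is a reason to reconcile the sections.

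Second, Table 11 is descriptive, no test is planned, and its first row gives the number of surgical procedures by arm. Recording only related non-serious events is a choice open to a pragmatic trial. This stands as far as it goes, but the procedure row does not restore events never entered before ablation, and the title does not disclose the filter.

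Three stronger readings are tempting and are not supported:

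- **A spurious difference is almost assured.** Take a 20% true rate, every early-arm event called related, and only 25–50% of compression-arm events recordable. The table would show 20% v 5–10%, nominally significant in 85% to over 99% of trials of 225 per arm. The arithmetic is right, but full attribution in the early arm is an extreme assumption and the test is not planned.
- **The cost comparison inherits the bias.** Protocol 7.5 costs resource use recorded for each patient at each follow-up, and resource use is on the telephone schedule for all patients. Nothing says that costs come from the filtered entries.
- **Any benefit of early ablation is hidden.** Healing is judged blind, recurrence is followed monthly in both arms, and SAEs to 12 months are recorded regardless of relatedness. The gap is confined to non-serious events.

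**Conclusion.** The point holds in a limited form. As written, the plan passes non-serious adverse events through an unblinded relatedness judgement and then presents them by randomised arm without saying so. Listed events that also occur under compression alone, including non-serious DVT, are likely to be under-recorded in compression-arm patients before ablation. Table 11 therefore cannot be taken as an unbiased between-arm comparison.

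The distortion can be anything from none to large. It is set by attribution in each arm, which the documents do not fix, and the ratios of 1.0 to 2.0 shown above rest wholly on assumed attribution and event rates. The primary outcome, the SAEs to 12 months in Table 12 and the costing are not shown to be affected.

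**What to change.** Preferred: reconcile Protocol 8.1 to 8.3 so that the events listed in 8.2 are recorded in both arms for 12 months whatever their judged relatedness. State what the interventions are, hold relatedness as a separate field, and add that field to SAP Table 11. The cost is a modest increase in entries from telephone calls that already include an adverse-event assessment.

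If collection cannot change, amend the SAP only. Retitle Table 11 as intervention-related non-serious adverse events, report the counts against the number of endovenous procedures in each arm (the table already has a procedure row), and state in SAP 4.8 that no between-arm comparison of non-serious events is made. This needs no new data. It does not recover unrecorded events, but it stops the table from being read as something it is not.

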8.4 SERIOUS ADVERSE EVENTS

In addition to clinical assessments, patients will be contacted on a monthly basis by telephone for 12 months to identify any additional treatments, admissions or other complications related to their leg ulceration. Unrelated serious adverse events will also be recorded and reported in accordance with the Good Clinical Practice guidance up to 12 months. Serious adverse events (SAE) are defined as those adverse events that: result in death; are life-threatening; require in-patient hospitalisation or prolongation of existing hospitalisation; result in persistent or significant disability or incapacity; result in congenital anomaly or birth defect; are cancer; or are other important medical events in the opinion of the responsible investigator (i.e. not life threatening or resulting in hospitalisation, but may jeopardise the participant or require intervention to prevent one or more of the outcomes described previously).

All SAEs reported by participants at (or between) each follow-up visit will be recorded by local researchers and entered into InForm within 24 hours of the researcher becoming aware of the event.

All SAEs will be reported by the trial manager to the Sponsor and Chair of the Data Monitoring Committee. Related and unexpected SAEs will also be reported to the relevant Ethics Committee.

In the event that InForm is not accessible notify the Trial Manager, [name]:

[contact] (Mon to Fri 09.00 – 17.00)

Email: [contact]

9. REGULATORY ISSUES

9.1 ETHICS APPROVAL

After approval from the Research Ethics Committee, the study must be submitted for Site Specific Assessment (SSA) at each participating NHS Trust. The Chief Investigator will require a copy of the Trust R&D approval letter before accepting participants into the study. The study will be conducted in accordance with the recommendations for physicians involved in research on human subjects adopted by the 18th World Medical Assembly, Helsinki 1964 and later revisions.

9.2 CONSENT

Consent to enter the study must be sought from each participant only after a full explanation has been given, an information leaflet offered and time allowed for consideration. Signed participant consent should be obtained. The right of the participant to refuse to participate without giving reasons must be respected. After the participant has entered the study the clinician remains free to give alternative treatment to that specified in the protocol at any stage if he/she feels it is in the participant's best interest, but the reasons for doing so should be recorded. In these cases the participants remain within the study for the purposes of follow-up and data analysis. All participants are free to withdraw at any time from the protocol treatment without giving reasons and without prejudicing further treatment. Patients will not be specifically reconsented for the collection data in October 2018 as they already consented for the collection of longer term data at the outset. Patients will be asked, however at the telephone contact if they wish to continue in the study.

